### **Best Overall Response**

BOR is defined as the best response designation, as determined by BICR, recorded between the date of randomization and the date of progression, as assessed by BICR per RECIST 1.1, or the date of subsequent anticancer therapy (including tumor-directed radiotherapy and tumor-directed surgery), whichever occurs first. For subjects without evidence of RECIST 1.1 progression or subsequent anticancer therapy, all available response designations will contribute to the BOR assessment. For subjects who continue treatment beyond progression, the BOR will be determined based on response designations up to the time of initial RECIST 1.1 progression.

Tumor assessments should occur every 6 weeks ( $\pm 1$  week) for the first 48 weeks, then every 12 weeks ( $\pm 1$  week) until disease progression or subsequent therapy (whichever occurs later).

### **Duration of Objective Response**

Duration of Objective Response (DOR) is defined as the time between the date of first confirmed response (CR or PR) to the date of the first documented progression as determined by BICR (per RECIST 1.1), or death due to any cause, whichever occurs first. Subjects who neither progress nor die will be censored on the date of their last evaluable tumor assessment. Subjects who started any subsequent anti-cancer therapy without a prior reported progression will be censored at the last evaluable tumor assessment prior to or on initiation of the subsequent anti-cancer therapy. DOR will be evaluated for responders (i.e. subjects with confirmed CR or PR) only.

### **Time to Objective Response**

Time to Objective Response (TTR) is a supporting endpoint for ORR. TTR is defined as the time from randomization to the date of the first confirmed response (CR or PR), as assessed by BICR. TTR will be evaluated for responders (i.e. subjects with a BOR of confirmed CR or PR) only.

## **4.2 Secondary Endpoints**

### **4.2.1 Objective Response Rate by BICR and Duration of Objective Response in Platinum Eligible Subgroup**

The secondary endpoints of ORR and DOR by BICR in platinum eligible subgroup are defined similarly as described for the primary endpoint.

### **4.2.2 Progression-free Survival by BICR**

#### **4.2.2.1 Primary Definition of Progression-free Survival by BICR**

[figure not shown]
The BICR-assessed PFS is defined as the time from randomization to the date of first documented disease progression, as assessed by the BICR using RECIST 1.1 criteria, or death due to any cause, whichever occurs first. Subjects who died without a reported progression will be considered to have progressed on the date of their death. Subjects who did not progress or die will be censored

on the date of their last evaluable tumor assessment. Subjects who did not have any on study tumor assessments and did not die will be censored on the date they were randomized. Subjects who started any subsequent anti-cancer therapy, including tumor-directed radiotherapy and tumor-directed surgery, without a prior reported progression will be censored on the date of their last evaluable tumor assessment prior to/on the initiation of the subsequent anti-cancer therapy.

- For subjects without any baseline TA, they will be censored at randomization date
- For subjects with baseline TA but without any on study TA, if no death information is available, subjects will be censored at randomization date; if death information is available, subjects will be either an event at death date if no subsequent therapy is in the record or censored at randomization date if subsequent therapy exists.
- For subjects with baseline and on-study TA,
  - a) Subjects who did not have disease progression per BICR assessment or die will be censored on the date of last tumor assessment on study if there's no subsequent therapy or last tumor assessment conducted on/prior to the subsequent therapy if there's one.
  - b) Subjects who did have disease progression per BICR assessment or die will be an event at disease progression per BICR assessment or death date if there's no subsequent therapy before the event or censored at the last tumor assessment date conducted on/prior to the subsequent therapy date.

Further explanation for various censoring scenarios for the primary definition of PFS are presented in [Figure 4.2.2.1-1](#).

**Figure 4.2.2.1-1: Graphic display of PFS Primary Definition**

**4.2.2.2 Secondary Definition of Progression-free Survival by BICR**

The secondary definition of PFS (ITT definition) is the time between the date of randomization and the first date of documented progression, as determined by BICR (as per RECIST 1.1 criteria), or death due to any cause, whichever occurs first. Subjects who died without a reported progression will be considered to have progressed on the date of their death. A subject’s PFS time will not be censored for subsequent anti-cancer therapy prior to a progression event.

[figure not shown]
The following censoring rules will be applied for the secondary definition of PFS.

- For subjects without any baseline TA, they will be censored at randomization date
- For subjects with baseline TA but without any on study TA, if no death information is available, subjects will be censored at randomization date; if death information is available, subjects will be an event at death date.
- For subjects with baseline and on-study TA,
  - a) Subjects who did not have disease progression per BICR assessment or die will be censored on the date of last tumor assessment on study.
  - b) Subjects who did have disease progression per BICR assessment or die will be an event at disease progression per BICR assessment or death date.

Further explanation for various censoring scenarios for the secondary definition of PFS are presented in Figure 4.2.2.2-1.

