##### **2. Target Population**

- a. Histologically confirmed head and neck squamous cell carcinoma (SCCHN) from any of the following primary sites only: oral cavity, oropharynx, hypopharynx and larynx (including squamous cell carcinoma of unknown primary arising from head and neck if HPV p-16 positive).
- b. Must have metastatic or recurrent disease that is not amenable to therapy with curative intent (surgery or radiation therapy with or without chemotherapy). Subjects that refuse potentially curative salvage surgery for recurrent disease are ineligible.
- c. Two subgroups will be enrolled into this study, as detailed above. Subjects will be classified as platinum refractory or platinum eligible.

No prior treatment with systemic anti-cancer therapy for recurrent or metastatic SCCHN, except if given as adjuvant or neoadjuvant chemotherapy, or chemotherapy as part of multimodal (chemo, radiation) treatment for locally advanced disease.

- i. Platinum refractory subgroup (n = approximately 216): subjects with histologically confirmed SCCHN that has recurred during or less than 6 months after completion of previous platinum based chemotherapy, given as adjuvant or neoadjuvant treatment or as part of multimodal treatment (chemotherapy, surgery, radiotherapy) for locally advanced disease.
- ii. Platinum eligible subgroup (n = approximately 180): subjects with histologically confirmed SCCHN who are platinum naive or have recurred 6 months or more after completion of previous platinum-based chemotherapy, given as adjuvant or neoadjuvant treatment or as part of multimodal treatment (chemotherapy, surgery, radiotherapy) for locally advanced disease.

**[As of Revised Protocol 03, this criterion has been moved to 2.c]** *No prior treatment with systemic anti-cancer therapy for recurrent or metastatic SCCHN, except if given as adjuvant or neoadjuvant chemotherapy, or chemotherapy as part of multimodal (chemo, radiation) treatment for locally advanced disease.*

- d. Eastern Cooperative Oncology Group (ECOG) Performance Status of  $\leq 1$
- e. Measurable disease by computed tomography (CT) or magnetic resonance imaging (MRI) per RECIST 1.1 criteria; radiographic tumor assessment performed prior to randomization.
  - i. Target lesions may be located in a previously irradiated field if there is documented (radiographic) disease progression in that site after the completion of radiation therapy.

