### **8.3.2 Secondary Endpoint(s)**

The secondary endpoint of ORR and DOR in platinum eligible subgroup is defined similarly as described for the primary endpoint.

The BICR-assessed PFS is defined as the time from randomization to the date of first documented disease progression, as assessed by the BICR using RECIST 1.1 criteria, or death due to any cause, whichever occurs first. Subjects who died without a reported progression will be considered to have progressed on the date of their death. Subjects who did not progress or die will be censored on the date of their last evaluable tumor assessment. Subjects who did not have any on study tumor assessments and did not die will be censored on the date they were randomized. Subjects who started any subsequent anti-cancer therapy, including tumor-directed radiotherapy and tumor-directed surgery, without a prior reported progression will be censored at the last evaluable tumor assessment prior to/on initiation of the subsequent anti-cancer therapy.

OS is defined as the time between the date of randomization and the date of death. For subjects without documentation of death, OS will be censored on the last date the subject was known to be alive.

PD-L1 expression is defined as the percent of tumor cell membrane staining in a minimum of 100 evaluable tumor cells per validated Dako PD-L1 IHC assay.

The final analysis of the ORR in each of platinum eligible and platinum refractory subgroups will occur at least 9 months after the sufficient number of subjects in that subgroup have been randomized (approximately 180 in platinum eligible and 216 in platinum refractory subgroups). Analysis of the PFS and OS will also be performed at the same time as the ORR analysis.

[REDACTED]

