### **7.5.3 Progression Free Survival**

#### **7.5.3.1 PFS primary analysis**

The PFS function based on BICR assessment for each treatment arm will be estimated using Kaplan Meier technique and will be displayed graphically in the platinum refractory and platinum eligible subgroups, separately. The primary definition of PFS will be used in this analysis ([Section 4.2.2](#)). Median Survival time along with 95% CI will be constructed based on a log-log transformed CI for the survivor function. The hazard ratio and the 95% confidence interval will be estimated in a stratified Cox proportional hazards model using the randomized arm as a single covariate, stratified by PD-L1 status and HPV p-16 status, in the platinum refractory and platinum eligible subgroups, separately. PFS rates at 3, 6, 12 and 24 months, with 95% CIs will be estimated using Kaplan-Meier methodology. Minimum follow-up must be greater than or equal to the time-point to generate the rate.

The source of PFS event as assessed by BICR (RECIST 1.1 progression or death) will be summarized by treatment group.

The status of subjects who are censored (as per primary definition of PFS) in the PFS KM analysis will be tabulated for each randomized treatment group using the following categories:

- On-study (on-treatment, follow-up)
- Off-study (lost to follow-up, withdrawn consent, never treated)
- Received subsequent anticancer therapy

- No baseline tumor assessment

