### **7.5.3.2 Sensitivity Analyses of Progression Free Survival**

The following sensitivity analyses will be conducted using the primary definition of PFS in the randomized subjects:

- PFS per BICR using stratification factors as obtained from the baseline CRF pages and clinical database (instead of IVRS). The hazard ratio associated with treatment will be presented along with the associated two-sided 95% CIs. This analysis will be performed only if the stratification variable/factor at randomization (as per IVRS) and baseline are not concordant for at least 10% of randomized subjects.
- PFS per BICR using an un-stratified Cox model. The hazard ratio associated with treatment will be presented along with the associated two-sided 95% CIs.
- The primary PFS per BICR analysis will be repeated using secondary PFS definition which accounts for the tumor scans post subsequent therapies. The hazard ratio associated with treatment and median PFS will be presented along with the associated two-sided 95% CIs.

A by-subject listing for all randomized subjects will be presented including treatment arm, IVRS stratification level, PFS under the primary definition with censoring status and reason, PFS under the secondary definition with censoring status and reason.

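### Both SAP definitions of PFS censor subjects with no baseline tumor assessment at randomization without an exception for death, which contradicts the event rule stated just above the bullet (wrong as written; minor)

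*SAP*

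**What the plan says.** Protocol 8.3.2 defines BICR-assessed PFS as time to progression or death from any cause, and adds: "Subjects who died without a reported progression will be considered to have progressed on the date of their death". It allows censoring at randomization only when two conditions hold together: "Subjects who did not have any on study tumor assessments and did not die will be censored on the date they were randomized". The synopsis and Protocol 5.4.2 repeat these rules. None of the three ties anything to a missing baseline scan.

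SAP 4.2.2.1 (primary definition) restates both rules in its narrative. SAP 4.2.2.2 (secondary definition) begins "The secondary definition of PFS (ITT definition) is the time between the date of randomization and the first date of documented progression"; its narrative also makes a death without reported progression an event, and it drops censoring for subsequent therapy.

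Each section then gives a bulleted list of censoring rules. The first bullet is identical in both: "For subjects without any baseline TA, they will be censored at randomization date". The next bullet covers subjects who have a baseline scan but no on-study scan, and it does address death. In 4.2.2.2 it reads: "if death information is available, subjects will be an event at death date".

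SAP 7.5.3.1 lists "No baseline tumor assessment" among the categories for tabulating censored subjects. SAP 7.5.3.2 plans this sensitivity analysis: "The primary PFS per BICR analysis will be repeated using secondary PFS definition which accounts for the tumor scans post subsequent therapies".

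**The concern.** A death can be ascertained without a baseline scan, and the SAP already counts deaths in subjects who have no on-study scan at all. Neither document explains why a missing baseline scan should cancel a death. As the text stands, a programmer cannot follow both the narrative and the first bullet, and following the bullet departs from the protocol's definition of a named secondary endpoint without saying so.

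A subject censored on day 0 contributes nothing to the risk set, so an analysis specified for all randomized subjects leaves that person out in effect. If such subjects tend to deteriorate early, the reported PFS curve would sit too high. The same definitions would presumably also govern the PFS estimates planned at the interim analysis (SAP 7.5.6).

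**Working it through.** The plan states no PFS event count, power or expected share of subjects without a baseline scan, so there is no figure to reproduce. The check has two parts.

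**1. The rules applied to one subject.** Take a randomized subject with no baseline scan, no on-study scan and no subsequent therapy, who dies at time t.

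| Source | Result |
|---|---|
| Protocol 8.3.2 | event at t |
| SAP 4.2.2.1, narrative | event at t |
| SAP 4.2.2.1, first bullet | censored at day 0 |
| SAP 4.2.2.2, narrative | event at t |
| SAP 4.2.2.2, first bullet | censored at day 0 |

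Could the bullet be shorthand for censoring unless the subject died? Two features tell against that. The neighbouring bullet in each list spells out what happens on death, so the authors stated the condition where they intended it. SAP 7.5.3.1 also gives missing baseline assessment its own row as a reason for censoring, so the rule is meant to be applied.

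Three sensitivity analyses can be read in SAP 7.5.3.2: strata from the CRF and clinical database, an unstratified Cox model, and the secondary definition. The first two keep the primary definition and the third uses the secondary one. All three carry the bullet.

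**2. Size, with every share and rate assumed.**

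*Events lost.* The upper bound is N × m, where m is the share with no baseline scan and all of them are taken to die without prior subsequent therapy. With N = 216 platinum refractory subjects (Protocol 8.1):

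- m = 1%: 216 × 0.01 = 2.2
- m = 2%: 216 × 0.02 = 4.3

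For all 396 subjects the same shares give 4.0 and 7.9. If only 30% to 70% of affected subjects die without prior subsequent therapy, the totals among 396 fall to about 1 to 3 (m = 1%) and 2 to 6 (m = 2%).

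*Shift in the median.* Assume exponential PFS with a 3-month median in subjects who have a baseline scan, and an exponential time to death with median d months in those who do not. Counting the deaths, the median t solves

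(1 − m) × 0.5^(t/3) + m × 0.5^(t/d) = 0.5.

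Under the bullet, the affected subjects leave the risk set on day 0 and the median is 3.00 months.

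| m | d = 3 months | d = 1 month |
|---|---|---|
| 1% | 3.00 | 2.97 |
| 2% | 3.00 | 2.94 |

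With d = 3 the median does not move and only events are lost. With d = 1 the bullet overstates the median by 0.03 to 0.06 months, or about 1 to 2 days at the SAP's 30.4375 days per month.

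**The case against.** The strongest reply is that the group should be nearly empty and nothing depends on it. Protocol 3.4.1 (Target Population) requires measurable disease with "radiographic tumor assessment performed prior to randomization", and Protocol 3.4.2 allows no exceptions to eligibility. SAP section 5 says that no secondary endpoint will be tested, and OS counts every death. The handling is also traceable: SAP 7.5.3.1 tabulates missing baseline assessment as a censoring reason by arm, and SAP 7.5.3.2 lists each subject's censoring status and reason under both definitions. All of this stands. It limits the size of the effect, but it does not reconcile the bullet with the narrative.

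The two explanatory figures (4.2.2.1-1 and 4.2.2.2-1) are not reproduced in the text available and might add a death branch. Even so, the bullet as worded would still need correcting.

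Four stronger readings are tempting, and the documents do not support them.

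- *The ITT-labelled definition was meant to remove every exclusion.* The only purpose that the SAP states for it is to stop censoring for subsequent therapy. The protocol has no such definition, so for 4.2.2.2 the conflict is with the SAP's own narrative, and the label sits awkwardly with the bullet.
- *No planned PFS analysis counts these deaths.* The text of 7.5.3.4 and 7.5.3.5 (subset analyses and PFS by investigator) is redacted, so this can be said only of the analyses in 7.5.3.2.
- *PFS is overstated.* That holds only if affected subjects die earlier than the others.
- *The arm comparison is biased.* Whether a baseline scan exists is settled before treatment in a randomized, double-blind trial, and nothing in the documents suggests that the omission would favor either arm.

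**Conclusion.** The point holds as a contradiction in the text: wrong as written, minor severity. For any subject with no baseline scan who dies (under the primary definition, with no earlier subsequent therapy), the first bullet in SAP 4.2.2.1 and 4.2.2.2 drops an event that the same section's narrative counts. For the primary definition it also departs from Protocol 8.3.2.

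The practical effect is probably small. The magnitudes rest on an assumed 1% to 2% without a baseline scan, and the event counts of about 2 to 4 of 216 are upper bounds. The median shift of 1 to 2 days further assumes exponential times and a 1-month death median in affected subjects against 3 months in the rest. With equal death rates the curve is not shifted.

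**What to change.** In SAP 4.2.2.1 and 4.2.2.2, reword the first bullet so that subjects without any baseline assessment are censored at randomization only if they did not die. If they died, the death is an event on the death date; under the primary definition this applies only if no subsequent anti-cancer therapy came first. Check that Figures 4.2.2.1-1 and 4.2.2.2-1 agree with the revised rule. If the sponsor intends the present rule, the SAP should say that it departs from the protocol and explain why.

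The cost is one sentence in each of two sections and a small change to the PFS derivation program. No new data are needed.

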**Figure 4.2.2.2-1: Graphic Display of PFS Secondary Definition**

### 4.2.2.3 Progression-free survival rate

The progression free survival rate at time  $T$  is defined as the probability that a subject has not progressed and is alive at time  $T$  following randomization.

Tumor assessments should occur every 6 weeks ( $\pm 1$  week) for the first 48 weeks, then every 12 weeks ( $\pm 1$  week) until disease progression or subsequent therapy (whichever occurs later).

### 4.2.3 Overall Survival

OS is defined as the time between the date of randomization and the date of death. For subjects without documentation of death, OS will be censored on the last date the subject was known to be alive. The overall survival rate at time  $T$  is defined as the probability that a subject is alive at time  $T$  following randomization.

[REDACTED]

[REDACTED]

[REDACTED]

[REDACTED]

[REDACTED]

[REDACTED]

[REDACTED]

[REDACTED]

[REDACTED]

[REDACTED]

[REDACTED]

[REDACTED]

[REDACTED]

[REDACTED]

[REDACTED]

[REDACTED]

[REDACTED]

[Redacted]

[Redacted]

[Redacted]

## 5 SAMPLE SIZE AND POWER

The primary objective is to compare the ORR of nivolumab in combination with ipilimumab vs nivolumab in combination with ipilimumab placebo, as determined by BICR using Response Evaluation Criteria In Solid Tumors (RECIST 1.1) criteria in platinum refractory subjects with recurrent or metastatic SCCHN. The alpha level for the ORR is adjusted for one planned interim analysis using Lan-DeMets alpha spending function with O’Brien-Fleming boundaries, which will be determined by the fraction of subjects included in the interim analysis. Given that the interim analysis for the primary endpoint is expected to be performed when 70% of platinum refractory subjects have reached 6 months follow up after randomization, the alpha level is expected to be 0.015 for the interim analysis and 0.045 for the final analysis.

Approximately 396 subjects (216 platinum refractory subjects and 180 platinum eligible subjects) will be randomized to either nivolumab plus ipilimumab or nivolumab in combination with ipilimumab placebo in a 2:1 ratio.

A sample size of 216 randomized platinum refractory subjects (144 and 72 respectively) will provide 84% power for testing the odds ratio of nivolumab plus ipilimumab over Nivolumab in combination with placebo, with a 0.050 two-sided significance level, assuming ORR of 35% and 15% (odds ratio of 3.051) in the nivolumab plus ipilimumab and nivolumab in combination with ipilimumab placebo treatment group respectively (odds ratio of proportions test using EAST v6).

Only the primary endpoint will be tested, none of the secondary endpoints.

The first secondary objective is to estimate the ORR of the treatment of nivolumab in combination with ipilimumab vs nivolumab in combination with ipilimumab placebo, as determined by BICR using RECIST 1.1 criteria for first line treatment of recurrent or metastatic SCCHN in the platinum eligible setting.

Approximately 180 subjects (120 and 60 respectively) will be randomized in the platinum eligible subgroup. For a sample size of 120 subjects randomized to nivolumab plus ipilimumab, the maximum width of the exact two-sided 95% confidence interval (CI) is 18.6% when the ORR is expected to be in the 10% to 55% range. The table below summarizes the 95% exact CI when observed ORRs are between 10% and 55% respectively.

Table 5-1: Observed ORR with Exact 95% CI in Platinum Eligible Subjects randomized to nivolumab plus ipilimumab (N=120).

